11.2. Appendix 2: Study Phases and Treatment Emergent Adverse Events

11.2.1. Study Phases for Concomitant Medication

Study Phase	Definition
Prior	If medication end date is not missing and is prior to screening visit
Concomitant	Any medication that is not a prior

NOTES:

- Please refer to [Appendix 5: Reporting Standards for Missing Data](#) for handling of missing and partial dates for concomitant medication. Use the rules in this table if concomitant medication date is completely missing.

11.2.2. Treatment Emergent Flag for Adverse Events

Flag	Definition
Treatment Emergent	
 • If AE onset date is on or after study treatment start date (for that period) & on or before nemiralisib treatment stop date (for that period) plus 10 days (5 times half life of nemiralisib). • Study Treatment Start Date (for that period) \leq AE Start Date \leq Nemiralisib Treatment Stop Date (for that period) + 10 days . • Where 'study treatment' start date (for that period) refers to the date of the first dose given in that period (i.e. nemiralisib for period 1 and itraconazole for period 2)

NOTES:

- If the study treatment stop date is missing, then the AE will be considered to be On-Treatment.
- Time of study treatment dosing and start/stop time of AEs should be considered, if collected.

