**Follow-up:**

Participants will be instructed to return for a follow-up visit 5-10 days after the last dose of itraconazole.

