## 5.5. Dose Justification

The chosen dose level of nemirisib in this study is 100 mcg delivered via the Ellipta device. This dose level has been chosen as it is within the current dose range chosen for investigation in the ongoing phase 2b study 200879 (50 to 750 mcg) and has previously demonstrated an adequately characterizable PK profile. The optimal efficacious dose is currently unknown but in a previous clinical study in patients (study PII116678 in exacerbating COPD patients) dosed at 1000 mcg/day (equivalent to 500 mcg using the Ellipta device and the formulation proposed in this Drug drug interaction [DDI] study) a positive primary endpoint was achieved (airway volume as measured by functional CT imaging). The 100 mcg dose level will provide an adequate exposure margin over pre-clinical exposure stopping criteria (based on toxicology No observed adverse event level [NOAEL] and toxicokinetics) should the exposure to nemirisib increase significantly when co-administered with a CYP3A4 inhibitor. Using the predicted exposure of nemirisib at 100 mcg in humans (extrapolated exposures of 0.41 ng/mL and 1.2 ng.h/mL for Cmax and AUC24 respectively) and using the 13 week dog NOAEL exposures (680 ug/kg/day NOAEL on week 13 for male and female combined of 21 ng/mL and 79 ng.h/mL respectively) gave margins of approximately 51-fold and 66-fold for Cmax and AUC24 respectively. These margins are considered to provide sufficient cover for any potential increase in nemirisib exposures that co-administration of itraconazole would be anticipated to cause. The analytical assay for nemirisib and the known exposure range over the proposed sampling regimen is deemed appropriate to fully characterise the profile out to 120 hours post dose in Period 1 and 144 hours post dose in Period 2, following a 100 mcg single dose. Preliminary data from an ongoing trial (207674 PK bridge study single doses phase 2b material) defined terminal elimination half-life to be approximately 40 hours with a Tmax observed in the sample taken immediately post dose (5 mins) which fell off rapidly in a biexponential manner. The long elimination half-life of nemirisib is the driver behind the length of the sampling regimen. Nemirisib is also an *in vitro* inhibitor of CYP3A4 (Ki of 4.2  $\mu$ M [GSK report reference [2017N345216\\_00](#)]) however as systemic concentrations are likely to be < 3 nM (1 ng/mL) following a single inhaled dose of only 100  $\mu$ g the inhibition is predicted to be negligible.

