### **9.2.1. Time Period and Frequency for Collecting AE and SAE Information**

- All SAEs will be collected from the signing of the ICF until the follow-up visit at the time points specified in the SoA (Section 2).
- All AEs will be collected from the start of treatment until the follow-up visit at the time points specified in the SoA (Section 2).
- Medical occurrences that begin before the start of study treatment but after obtaining informed consent will be recorded on the Medical History/Current Medical Conditions section of the case report form (CRF) not the AE section.
- All SAEs will be recorded and reported to the sponsor or designee immediately and under no circumstance should this exceed 24 hours, as indicated in [Appendix 4](#). The investigator will submit any updated SAE data to the sponsor within 24 hours of it being available.
- Investigators are not obligated to actively seek AEs or SAEs in former study participants. However, if the investigator learns of any SAE, including a death, at any time after a participant has been discharged from the study, and he/she considers the event to be reasonably related to the study treatment or study participation, the investigator must promptly notify the sponsor.

- The method of recording, evaluating, and assessing causality of AEs and SAEs and the procedures for completing and transmitting SAE reports are provided in [Appendix 4](#).

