11.4. Appendix 4: Derived and Transformed Data

11.4.1. General

Multiple Measurements at One Analysis Time Point

- The mean of the measurements will be calculated and used in any derivation of summary statistics but if listed, all data will be presented.
- Participants having both High and Low values for Normal Ranges at any post-baseline visit for safety parameters will be counted in both the High and Low categories of “Any visit post-baseline” row of related summary tables. This will also be applicable to relevant Potential Clinical Importance summary tables.

Study Day

- Calculated as the number of days from First Dose Date within the period in question (in period 1 this will be the date of dosing with nemiralisib; in period 2 this will be the date of first dosing with itraconazole):
 - Ref Date = Missing → Study Day = Missing
 - Ref Date < First Dose Date → Study Day = Ref Date – First Dose Date
 - Ref Date ≥ First Dose Date → Study Day = Ref Date – (First Dose Date) + 1

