11.4.3. Safety

Adverse Events
AE Time Since First Dose (Days)

• If AE start date/time < date/time of first dose then Time since first dose = date of first dose – AE start date• If AE start date/time \geq date/time of first dose then Time since first dose = AE start date – date of first dose+1• Missing if AE start date or date of first dose is missing.• Note: First dose will be the date of dosing with nemralisib in period 1 and the date of first dosing with itraconazole in period 2.
AE Duration (Days)

• AE end date – AE start date + 1• Missing if AE start date or end date is missing.
AE's of Special Interest

• Post-inhalation cough is an AE of special interest. The lower level term (LLT) to be included is "coughing after drug inhalation"

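### The SAP closes the Period 2 treatment-emergent window before AE collection ends, and its onset formula gives events dated before the first dose a positive time

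*SAP*

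**What the plan says.** **Treatment-emergent window.** SAP 11.2.2 starts the window on the study treatment start date, which "refers to the date of the first dose given in that period (i.e. nemiralisib for period 1 and itraconazole for period 2". The end depends on nemiralisib alone: onset must be "on or before nemiralisib treatment stop date (for that period) plus 10 days (5 times half life of nemiralisib". A note adds: "Time of study treatment dosing and start/stop time of AEs should be considered, if collected".

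**AE collection.** Protocol 9.2.1: "All AEs will be collected from the start of treatment until the follow-up visit". The Protocol synopsis: "Participants will be instructed to return for a follow-up visit 5-10 days after the last dose of itraconazole". Protocol 5.1 gives itraconazole on Days 1 to 10 of Period 2 and nemiralisib on Day 5, with at least 14 days between the two nemiralisib doses.

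**Stop date elsewhere in the SAP.** For partial AE dates, SAP 11.5.2.1 takes the stop date as the last dose in the period of whichever drug was given last.

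**Onset relative to dosing.** For an AE starting before the first dose, SAP 11.4.3 sets "Time since first dose = date of first dose – AE start date". For a date before the first dose, SAP 11.4.1 sets "Study Day = Ref Date – First Dose Date".

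**The concern.** The Period 2 window starts with one drug and ends with the other. Itraconazole is also a study treatment and continues for five days after the nemiralisib dose, yet the closing date ignores it. Protocol 3.3.1 lists increased hepatic enzymes and arrhythmia among itraconazole's most common reactions. After Day 10 the only scheduled chemistry and ECG are at follow-up. An AE first recognised there, with its onset recorded as the visit date, would usually fall outside the window.

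The onset formula is a separate slip. Its pre-dose branch returns positive numbers, so the derived time alone cannot separate an event before dosing from one after it. Two sections of the same SAP then give opposite signs for the same date.

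AEs are among the secondary safety endpoints and are summarised by treatment. At stake is whether the flag and the onset variable mean what a reader of the dataset or listings will take them to mean.

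**Working it through.** **The plan's own figure.** SAP 11.2.2 describes 10 days as five half-lives. The protocol's preliminary data "defined terminal elimination half-life to be approximately 40 hours" (Section 5.5).
- 5 × 40 h = 200 h; 200 / 24 = 8.3 days, so the figure does not reproduce.
- 10 days = 240 h; 240 / 40 = 6 half-lives. Ten days would be five half-lives at 48 h, a value the documents do not give.
- The difference is on the long side for nemiralisib given alone.

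**Period 2 window.** Inputs: nemiralisib on Day 5; last itraconazole dose on Day 10 (Protocol 5.1); follow-up 5 to 10 days after that dose.
- Close = 5 + 10 = Day 15.
- Follow-up = Day 10 + 5 to Day 10 + 10 = Days 15 to 20.
- Visit days after close: Days 16 to 20, or 5 of 6.
- Cover after the last itraconazole dose: 15 − 10 = 5 days.

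Sensitivity: the itraconazole row of the Period 2 schedule, as extracted, has nine marks (Days 1 to 9). This may be an extraction fault; if not, the row and the text must be reconciled. With a last dose on Day 9, follow-up is Days 14 to 19, and Days 16 to 19 fall after close, or 4 of 6.

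**Period 1 window.** Let D be the Period 1 dose date, so the window closes on D + 10. Period 2 nemiralisib is given w days after D, on Period 2 Day 5, so Period 2 Day 1 = D + w − 4.

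| w (days) | Period 2 Day 1 | Dates in both windows | Dates in neither window |
|---|---|---|---|
| 14 | D + 10 | 1 | 0 |
| 15 | D + 11 | 0 | 0 |
| 16 | D + 12 | 0 | 1 |

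If clock times are used, the overlap at w = 14 shrinks to about one hour. Nemiralisib is given at about the same time in both periods, and itraconazole precedes it by one hour.

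**Onset formula.** Offset = AE start date minus first dose date.

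| Offset (days) | SAP 11.4.3 | SAP 11.4.1 |
|---|---|---|
| −3 | +3 | −3 |
| −2 | +2 | −2 |
| −1 | +1 | −1 |
| 0 (after dose) | +1 | 1 |
| 1 | +2 | 2 |
| 2 | +3 | 3 |

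An AE on the dosing date but before the dose gets 0 under 11.4.3.

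**Check of the remedy.** Last dose of either drug + 10 = Day 20 (Day 19 if the last dose is Day 9). That is the last permitted visit day, so no permitted visit day falls outside. Reversing the pre-dose subtraction gives −1, −2 and −3, in line with 11.4.1.

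**The case against.** The strongest objection is that nothing is shown to be lost. The planned AE tables (SAP 11.8.7) cover all AEs and all drug-related AEs, and the AE listings (11.8.8) are not restricted by title to treatment-emergent events. No listed display names the flag, and the shells are not included. A reader might infer that late events would vanish from the report; the documents do not support that. A raised ALT or an ECG change at follow-up also has its own laboratory, liver and ECG tables and listings, which are not stated to depend on the AE flag. This stands, and it limits the point to the correctness of the rule.

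Further limits also stand:
- The flag uses onset, not the visit date. An AE reported on Day 20 with onset by Day 15 is still flagged. Five of six is a count of permitted visit days, not a share of visits or events.
- The overlap needs exactly 14 days between doses. A reader might infer that an itraconazole-day event would be credited to nemiralisib alone; the SAP does not say how an event in both windows is assigned.
- The sign slip does not reach every pre-dose event. A same-date pre-dose event gets 0, and non-serious events before first treatment go to medical history (Protocol 9.2.1). What remains is mainly pre-dose SAEs and between-period events measured against Period 2 dosing.
- SAP 11.5.2.1 serves partial-date imputation, so its broader stop date does not by itself override 11.2.2. The sections still use two meanings of the term.
- Protocol 10.3.2 has AEs listed and summarised by treatment. No formal comparison is planned.

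It is also tempting to argue that 10 days is too short because itraconazole may lengthen the half-life. If it doubled to 80 h (an assumption), five half-lives would be 400 h = 16.7 days after Day 5, past the latest follow-up. That is beyond AE collection, so no window could capture it, and the point does not rest on it.

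**Conclusion.** Two rules are wrong as written, and one boundary needs tidying.

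1. The Period 2 window closes while AEs are still being collected. Onsets from Day 16 to the follow-up visit are unflagged, a stretch of up to five days. This takes Day 10 as the last itraconazole dose and follow-up within its permitted range; with Day 9 the stretch is up to four days.
2. The pre-dose branch in 11.4.3 conflicts with 11.4.1 and produces values identical to post-dose ones. This follows from the formulas alone. Few events are likely to be touched in healthy volunteers.
3. The overlap is minor: one date at the 14-day minimum, about an hour with clock times, and none from 15 days.

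The documents show neither how many AEs would be affected nor that any table would change. The correction is worth making because a pre-specified flag and onset time should be right wherever they are used, and the cost is small.

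**What to change.** - **SAP 11.2.2, Period 2:** end the window at the follow-up visit. Last dose of either study drug plus 10 days gives the same flags for AEs collected from anyone who completes dosing and is seen within the permitted visit range. Use one definition of stop date here and in 11.5.2.1, and correct or remove the five-half-lives explanation of the 10 days.
- **SAP 11.2.2, Period 1:** end the window at nemiralisib plus 10 days or just before the first Period 2 itraconazole dose, whichever comes first. State that an AE on that date with no recorded time belongs to Period 2.
- **SAP 11.4.3:** for AEs before the first dose, use AE start date minus date of first dose. State which period's first dose applies to an AE starting between periods.
- **SAP 11.8:** state which displays, if any, use the flag.

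The cost is SAP wording and a few lines of derivation code, with no new data. Slightly more AEs may be flagged. The periods also become less alike: the Period 2 window grows from 15 days (Days 1 to 15) to as many as 20, while Period 1 stays at 11 days, or 10 when capped at the minimum interval. A footnote giving the two window lengths would tell readers of any by-treatment AE summary.

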11.3. Appendix 3: Data Display Standards & Handling Conventions

11.3.1. Reporting Process

Software	

 The currently supported versions of SAS software will be used. 	
Reporting Area	
HARP Server	: uk1salx00175
HARP Compound	: GSK2269557/mid206874
Analysis Datasets	

 Analysis datasets will be created according to CDISC standards (SDTM IG Version v3.2 & ADaM IG Version 1.0). 	
Generation of RTF Files	

 RTF files will be generated for the final reporting effort. 	

11.3.2. Reporting Standards

General

 The current GSK Integrated Data Standards Library (IDSL) will be applied for reporting, unless otherwise stated (IDSL Standards Location: https://spope.gsk.com/sites/IDSLLibrary/SitePages/Home.aspx): 
 4.03 to 4.23: General Principles 5.01 to 5.08: Principles Related to Data Listings 6.01 to 6.11: Principles Related to Summary Tables 7.01 to 7.13: Principles Related to Graphics
Formats

 GSK IDSL Statistical Principles (5.03 & 6.06.3) for decimal places (DP's) will be adopted for reporting of data based on the raw data collected, unless otherwise stated. Numeric data will be reported at the precision collected on the eCRF. The reported precision from non eCRF sources will follow the IDSL statistical principles but may be adjusted to a clinically interpretable number of DP's.
Planned and Actual Time

 Reporting for tables, figures and formal statistical analyses: 
 Planned time relative to dosing will be used in summary figures, summaries, statistical analyses and calculation of any derived parameters. Actual relative time will be used in subject plots and for the derivation of PK parameters. The impact of any major deviation from the planned assessment times and/or scheduled visit days on the analyses and interpretation of the results will be assessed as appropriate. Reporting for Data Listings: 
 Planned and actual time relative to study drug dosing will be shown in listings (Refer to IDSL Statistical Principle 5.05.1). Unscheduled or unplanned readings will be presented within the subject's listings.
Unscheduled Visits

 Unscheduled visits will not be included in summary tables or figures. All unscheduled visits will be included in listings.

Listings	

 Since this is a single sequence study, there is no need to include 'Sequence' or 'Arm' in any of the listings. 	
Descriptive Summary Statistics	
Continuous Data	Refer to IDSL Statistical Principle 6.06.1
Categorical Data	N, n, frequency, %
Graphical Displays	

 Refer to IDSL Statistical Principles 7.01 to 7.13. 	

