#### 8.1.2. QTc Stopping Criteria

A participant that meets either bulleted criterion based on the average of triplicate ECG readings will be withdrawn from study treatment.

- QTcF >500 msec,
- Change from baseline: QTcF >60 msec

The decision to withdraw a participant will be based on an average QTcF value of triplicate ECGs. If an ECG demonstrates a prolonged QTcF, obtain 2 more ECGs over a brief period (5–10 minutes), and then use the averaged QTcF values of the 3 ECGs to determine whether the participant should be discontinued from the study.

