### **8.1.5. Temporary Discontinuation**

A participant withdrawn from the study treatment will no longer continue in the trial.

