## 12.6. Appendix 6: Liver Safety: Required Actions and Follow-up Assessments

### Phase I liver chemistry stopping criteria and required follow up assessments

Liver Chemistry Stopping Criteria	
Required Actions and Follow up Assessments	
Actions	Follow Up Assessments

ALT-absolute
 
ALT<math>\geq</math>3xULN
 
If ALT<math>\geq</math>3xULN AND bilirubin <math>\geq</math>2xULN (>35% direct bilirubin) or INR <math>></math>1.5, Report as an SAE.
 
See additional Actions and Follow Up Assessments listed below
	
 
• Immediately discontinue study treatment
 
• Report the event to GSK within 24 hours
 
• Complete the liver event CRF, and complete an SAE data collection tool if the event also meets the criteria for an SAE
 
• Perform liver event follow up assessments
 
• Monitor the subject until liver chemistries resolve, stabilise, or return to within baseline (see MONITORING below)
 
 
MONITORING:
 
If ALT<math>\geq</math>3xULN AND bilirubin <math>\geq</math> 2xULN or INR <math>></math>1.5
 
 
• Repeat liver chemistries (include ALT, AST, alkaline phosphatase, bilirubin) and perform liver event follow up assessments within 24 hrs
 
• Monitor subjects twice weekly until liver chemistries resolve, stabilise or return to within baseline
 
• A specialist or hepatology consultation is recommended
 
 
If ALT<math>\geq</math>3xULN AND bilirubin <math><</math>2xULN and INR <math>\leq</math>1.5:
 
 
• Repeat liver chemistries (include ALT, AST, alkaline phosphatase, bilirubin) and perform
 
 
 
• Viral hepatitis serology
 
• Obtain INR and recheck with each liver chemistry assessment until the transaminases values show downward trend
 
• Obtain blood sample for pharmacokinetic (PK) analysis, obtained within 7 days of last dose
 
• Serum creatine phosphokinase (CPK) and lactate dehydrogenase (LDH).
 
• Fractionate bilirubin, if total bilirubin<math>\geq</math>2xULN
 
• Obtain complete blood count with differential to assess eosinophilia
 
• Record the appearance or worsening of clinical symptoms of liver injury, or hypersensitivity, on the AE report form
 
• Record use of concomitant medications on the concomitant medications report form including acetaminophen, herbal remedies, other over the counter medications.
 
• Record alcohol use on the liver event alcohol intake case report form
 
 
If ALT<math>\geq</math>3xULN AND bilirubin <math>\geq</math>2xULN or INR <math>></math>1.5:
 
 
• Anti-nuclear antibody, anti-smooth muscle
 

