5.2. Baseline Definitions

For all endpoints (except as noted in baseline definitions below) the baseline value will be the latest pre-dose assessment with a non-missing value, for the relevant period, including those from unscheduled visits. If time is not collected, Day 1 assessments are assumed to be taken prior to first dose and used as baseline. Note that baseline for FEV1 is defined as the screening visit in the protocol; however it is not required in any data displays so is not included here.

Parameter	Study Assessments Considered as Baseline		Baseline Used in Data Display
	Screening	Day 1 (Pre-Dose) [Periods 1 and 2]	
Safety			
Vital Signs	X ¹	X	Day 1 predose for the relevant period
ECG	X ¹	X	Day 1 predose for the relevant period

[1] Triplicate

Unless otherwise stated, if baseline data is missing no derivation will be performed and baseline will be set to missing.

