11.5. Appendix 5: Reporting Standards for Missing Data

11.5.1. Premature Withdrawals

Element	Reporting Detail
General	
 Subject study completion (i.e. as specified in the protocol) was defined as completing all phases of the study including the last visit. Withdrawn subjects may be replaced in the study. All available data from participants who were withdrawn from the study will be listed and all available planned data will be included in summary tables and figures, unless otherwise specified.

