11.8.7. Safety Tables

Safety: Tables					
No.	Population	IDSL / Example Shell	Title	Programming Notes	Deliverable [Priority]
Adverse Events (AEs)					
3.1.	Safety	AE1CP /	Summary of All Adverse Events by System Organ Class and Preferred Term	ICH E3	SAC
3.2.	Safety	AE1CP	Summary of All Drug-Related Adverse Events by System Organ Class and Preferred Term	ICH E3	SAC
Laboratory: Chemistry					
3.3.	Safety	LB1	Summary of Chemistry Changes from Baseline	ICH E3 Include baseline values. Add Footnote: 'Nemirisib was administered on Day 1 of Period 1 and Day 5 of Period 2'.	SAC
Laboratory: Hematology					
3.4.	Safety	LB1	Summary of Hematology Changes from Baseline	ICH E3 Include baseline values. Add Footnote: 'Nemirisib was administered on Day 1 of Period 1 and Day 5 of Period 2'.	SAC
Laboratory: Urinalysis					
3.5.	Safety	UR3b	Summary of Urine Dipstick Results	ICH E3 Add Footnote: 'Nemirisib was administered on Day 1 of Period 1 and Day 5 of Period 2'.	SAC

Safety: Tables					
No.	Population	IDSL / Example Shell	Title	Programming Notes	Deliverable [Priority]
Laboratory: Hepatobiliary (Liver)					
3.6.	Safety	LIVER1	Summary of Liver Monitoring/Stopping Event Reporting	IDSL	SAC
3.7.	Safety	LIVER10	Summary of Hepatobiliary Laboratory Abnormalities	IDSL	SAC
ECG					
3.8.	Safety	EG1	Summary of ECG Findings	IDSL Add Footnote: 'Nemiralisib was administered on Day 1 of Period 1 and Day 5 of Period 2'	SAC
3.9.	Safety	EG2	Summary of Change from Baseline in ECG Values by Visit	IDSL Include baseline values. Add Footnote: 'Nemiralisib was administered on Day 1 of Period 1 and Day 5 of Period 2'.	SAC
Vital Signs					
3.10.	Safety	VS1	Summary of Change from Baseline in Vital Signs	ICH E3 Include baseline values. Add Footnote: 'Nemiralisib was administered on Day 1 of Period 1 and Day 5 of Period 2'.	SAC

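### Read plainly, the SAP's exclusion of unscheduled visits can keep liver abnormalities first seen on protocol-mandated repeat tests out of Table 3.7 (minor)

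*SAP*

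**What the plan says.** SAP 11.3.2 sets one rule for all displays: "Unscheduled visits will not be included in summary tables or figures". Its companion sentence sends the same data elsewhere: "All unscheduled visits will be included in listings". SAP 11.5.1 has matching wording for withdrawn participants, where "all available planned data will be included in summary tables and figures", unless otherwise specified. No safety table is exempted. Baseline is treated differently: SAP 5.2 takes the latest non-missing pre-dose value, "including those from unscheduled visits".

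The table at issue is Table 3.7 in SAP 11.8.7, "Summary of Hepatobiliary Laboratory Abnormalities". Table 3.6 in the same section covers liver monitoring and stopping events.

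Protocol Appendix 6 sets the tests that follow ALT of at least 3xULN. If bilirubin is at least 2xULN or INR exceeds 1.5, the instruction is "Repeat liver chemistries (include ALT, AST, alkaline phosphatase, bilirubin) and perform liver event follow up assessments within 24 hrs", followed by twice-weekly monitoring. Otherwise the repeat falls at 24 to 72 hours and monitoring is weekly. INR is obtained as part of this follow-up. On participant status, Protocol 8.1.5 says "A participant withdrawn from the study treatment will no longer continue in the trial". Protocol 8.2 still expects the assessments planned for the follow-up visit.

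**The concern.** Raised hepatic enzymes are a named itraconazole risk in Protocol 3.3.1, and safety and tolerability form a secondary objective. A table of liver abnormalities is useful because it shows how far values rose and whether ALT rose together with bilirubin or INR. The protocol looks for exactly that in repeat tests outside the visit schedule, and the SAP's general rule removes those tests from summary tables.

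If a programmer follows the rule literally, Table 3.7 reports the sample that raised the alarm and omits the sample that showed how serious the event was. The table and the listings would then disagree about the same participant. The SAP also becomes hard to apply consistently. SAP 11.4.1 describes a row covering any post-baseline visit, but under 11.3.2 that row would not cover every visit.

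**Working it through.** The plan gives no figure to reproduce. The check sets the schedule beside the rule.

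**1. Scheduled liver chemistry.** In the Protocol schedule of activities (Tables 1 and 3), Period 2 chemistry is drawn on Days -1, 2, 4, 6, 8 and 10, then at follow-up 5 to 10 days after the last itraconazole dose.

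**2. When the repeats fall.** Suppose the Day 8 sample meets the stopping criterion.
- Repeat at 24 to 72 hours: Day 8 + 1 to Day 8 + 3 = Days 9 to 11. The more urgent repeat (within 24 hours) falls by Day 9.
- Follow-up if the last itraconazole dose was on Day 7: Day 7 + 5 to Day 7 + 10 = Days 12 to 17. If it was on Day 8: Days 13 to 18.
- The first repeat therefore comes before the earliest follow-up visit. The planned Day 10 sample does not rescue it, because under Protocol 8.1.5 the participant is no longer in the trial. Later weekly or twice-weekly tests are also unscheduled unless one coincides with follow-up.

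**3. INR.** The scheduled laboratory tests in Protocol Appendix 2 (Table 4) do not include INR. It is obtained only as liver-event follow-up. ALT of at least 3xULN with INR above 1.5 is nevertheless one of the two combinations the protocol treats as possible severe liver injury. Unless it is drawn at the follow-up visit, an INR result is unscheduled.

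**4. What the table would show (illustrative values).**

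| Sample | ALT | Bilirubin | Eligible for Table 3.7 under 11.3.2 |
|---|---|---|---|
| Scheduled, Day 8 | 3.2xULN | 1.4xULN | Yes |
| Mandated repeat | 6xULN | 2.1xULN, with more than 35% direct | No |

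The repeat meets the protocol's combined criterion (ALT at least 3xULN, bilirubin at least 2xULN, direct fraction above 35%) and must be reported as an SAE. Table 3.7 would draw only on the first row: ALT at or above 3xULN, with no combined case.

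**5. Size.** About 20 participants are planned, so one misclassified participant is 1/20 = 5.0%. The target of 16 evaluable participants is not the right denominator, because the Safety population is everyone dosed.

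**The case against.** Much of the case on the other side stands.

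- **The event is not hidden.** Appendix 6 requires a liver event CRF, and Table 3.6 is titled as event reporting, so it may count the event whatever the visit label. A possible Hy's Law case must be reported as an SAE, which brings it into the adverse event displays. SAP 11.3.2 itself puts every unscheduled result in the listings. A reader might infer that repeat liver results cannot reach any liver summary; the documents do not support that.
- **The participant is usually already counted.** If a scheduled sample triggers the stop, ALT of at least 3xULN is already in the table. What can be lost is a higher grade or a combined criterion first met later.
- **The shell is not available.** Table 3.7 follows shell LIVER10 under the sponsor's display standards, which the documents do not reproduce. It may draw on all post-baseline data. Against this, SAP 11.3.2 applies those standards unless otherwise stated, and the unscheduled-visit sentence is such a statement. The conflict is real, but its outcome cannot be settled from the documents.
- **SAP 11.5.1 is weak support.** It says that planned data are included, with a qualifier. It is not a separate prohibition.

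A reader might also infer that the ECG tables under-count the worst QTcF values, because Protocol 8.1.2 calls for two further ECGs after a prolonged reading. That is not established. Those ECGs are taken within 5 to 10 minutes, and SAP 11.4.1 averages multiple measurements at one analysis time point, so they may belong to the scheduled assessment. Table 3.9 is by visit, and no table of maximum QTcF is planned. Nor is the direction fixed. Illustrative readings of 505, 485 and 480 msec average 1470/3 = 490, so the first reading alone would overstate. Readings of 495, 510 and 512 average 1517/3 = 505.7, so it would understate. At most, Table 3.8 might miss an abnormal finding seen only on a repeat.

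**Conclusion.** The point holds for one table. Applied as written, SAP 11.3.2 can leave a peak ALT grade, or a combined ALT/bilirubin or ALT/INR criterion, out of Table 3.7 when it is first met on a repeat test. Each affected participant is about 5% of the roughly 20 planned, although such an event may well not occur in a trial this small.

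Two assumptions carry this conclusion: that the general sentence in 11.3.2 governs Table 3.7, and that the table grades ALT and shows combined criteria. Neither can be confirmed without the shell.

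The severity is minor. Safety is reported descriptively, the values remain in the listings, serious cases are reported as SAEs, and the primary PK analysis is untouched. For ECGs the documents show only an ambiguity about how confirmatory readings are assigned.

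**What to change.** In SAP 11.3.2, replace the blanket sentence with a rule by type of summary, and make 11.5.1 consistent with it:

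- By-visit summaries exclude unscheduled visits.
- Table 3.7, and any row covering any post-baseline visit under 11.4.1, use all post-baseline results in the period, including unscheduled and repeat values.

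A further clarification is worth adding in 11.4.1: state whether confirmatory ECGs belong to the scheduled time point and are averaged into it, or are treated as unscheduled.

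The cost is a few sentences before database freeze. No new data are needed, no clinical rule changes, and the liver wording leaves the by-visit tables as they are. The downside is that abnormality counts may be slightly less favourable. If confirmatory ECGs are averaged in, the by-visit QTcF values may move in either direction.
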